Sildenafil for Fontan Associated
Liver Disease (SiFALD) Study

NCT# 03154476

July 31, 2019

Sildenafil for Fontan Associated Liver Disease (SiFALD) study

IRB: 16-008985

NCT03154476

Fontan associated liver disease (FALD) affect 50% of all survivor of the Fontan operation, about 3 decades after the initial operation. It is associated with significant mortality and morbidity, and currently there are no treatment strategies to halt progression of this disease. The purpose of this study is to determine the efficacy of phosphodiesterase-5 inhibitor (sildenafil) in modifying the progression of FALD.

Principal Investigator:

[name], MPH

Co-investigators:

[name]

[name]

[name]

[name]

[name]

A. Rationale

Background

The Fontan operation is an effective surgical palliation for patients with complex cyanotic heart disease.¹ The physiologic benefit of the Fontan operation is that it separates the systemic and pulmonary circulations, thereby eliminating cyanosis and ventricular volume overload. However, the absence of a subpulmonary ventricle results in an obligatory high central venous pressure and low cardiac output state.^{2,3} These hemodynamic derangements result in chronic hepatic congestion and reduced blood supply to the liver.^{4,5} The downstream effect is a spectrum of Fontan associated liver diseases (FALD) such as liver fibrosis, cirrhosis and hepatocellular cancer.^{4,6-8}

Clinical and Public Health Significance

The prevalence of cirrhosis is 50% at 3 decades after their initial Fontan operation.^{6,8} The diagnosis of cirrhosis is a strong predictor of death in this population because more than two-thirds of the patients with cirrhosis are dead within 5 years.⁶ Those who survive experience significant morbidities such as variceal bleeding, hepatic encephalopathy, liver failure and hepatocellular cancer.

The incidence of complex cyanotic heart disease such as single ventricle diagnosis is 91 per 100,000 live births.^{9,10} Based on the annual birth rate of 4.2 million in the United States,¹¹ more than 4 thousand babies with complex single ventricle diagnosis are born every year, and most of them will undergo Fontan operation. More than 80% of patients undergoing Fontan

operation in the current era survive to adulthood, and most of these patients will develop FALD.¹²

[figure not shown]

Figure 1: Schematic showing the hemodynamic interaction between the liver and the Fontan circulation. Adapted from Poterucha et al.¹³

B. Hypothesis

The use of pulmonary vasodilators will promote forward flow in the Fontan circuit, reduce hepatic congestion and halt the progression of liver fibrosis.

C. Innovation

(i) Available data suggest that chronic hepatic congestion, inherent in the Fontan physiology, is the precursor of early liver fibrosis and cirrhosis in the Fontan population.^{2,3} A recent study based on the Mayo Clinic Fontan

cohort showed that half of the patients had liver fibrosis after 30 years from the time of initial Fontan.⁶

(ii) This proposed study would be the first study to assess the role of pulmonary vasodilators in the management of FALD.

D. Significance

(i) The adult congenital heart disease program at Mayo Clinic has the largest and oldest cohort of Fontan patients in the United States, and this places Mayo Clinic in a unique position to study this problem.

(ii) Data from this study will influence the management of FALD nationally and worldwide.

E. Brief Synopsis of Methods

(i) All patients enrolled in the study will undergo a baseline liver magnetic resonance elastography (MRE) prior to the initiation of phosphodiesterase-5 inhibitor (sildenafil).

(ii) A second MRE will be performed after 12 months of therapy.

F. Preliminary studies to support feasibility

(i) Several studies have shown that the use of pulmonary vasodilators in Fontan patients (even those with normal pulmonary vascular resistance) results in increased cardiac output and exercise tolerance by promoting forward flow in the Fontan circuit.¹⁴⁻¹⁶

(ii) A recent study from the Mayo Clinic showed that liver stiffness measured by MRE correlates with severity of fibrosis on liver biopsy.¹³

(iii) The proposed study is built on the foundation of these previous studies. Pulmonary vasodilators will be used to promote forward flow in the Fontan

circuit, and thereby reduce liver congestion. MRE will then be used to monitor treatment effect. We chose a phosphodiesterase-5 inhibitor instead of an endothelin receptor antagonist because the latter is associated with hepatotoxicity.

G. Study design

1. Inclusion criteria: All adult (age \geq 18 years old) Fontan patients who have no contraindications for magnetic resonance imaging (MRI) will be eligible for the study. Informed consent will be obtained from potential participants by their primary cardiologist or dedicated study personnel.
2. Exclusion criteria: Subjects with implantable pacemakers, residual cardiac lesions (severe ventricular dysfunction, severe atrioventricular valve regurgitation, Fontan baffle or conduit obstruction), viral hepatitis, severe renal dysfunction, a history of sildenafil use in the six months prior to study enrollment, ongoing sildenafil therapy, or patients currently taking nitrates. Based on the stipulation from the Food and Drug Administration regarding the approved use of sildenafil, we also excluded patients with hypotension at baseline (BP $<$ 80/50 mmHg), pulmonary veno-occlusive disease, and pulmonary hypertension due to sickle cell disease. Women of child-bearing potential with a positive pregnancy test will additionally be excluded.
3. All participants may undergo the following baseline tests (\pm 4 weeks) as part of standard clinical care: transthoracic echocardiogram, electrocardiogram, cardiopulmonary exercise test, complete blood count, chemistry panel, INR, alpha-fetoprotein. All these tests are routine clinical tests in the Mayo Clinic Adult Congenital Heart

- Disease program. Baseline clinical tests performed within 6 months prior to enrollment will be accepted as part of the study (data will be utilized if results are available). Any routine standard clinical tests or procedures that are not completed will not be considered a deviation.
4. Other additional baseline tests include:
 - a. MRI studies: [cardiac MRI + Liver MRE + 4D phase contrast imaging of the abdomen]
 - b. Abdominal ultrasound [full abdominal scan with Doppler of portal/hepatic/mesenteric vessels]
 - c. Biomarkers [NT-proBNP, ST2, Galectin-3, ADMA, ceramides, hs-CRP, Cystatin C, electrolytes]
 - d. Quality of life indices: MLHFQ: Minnesota Living with Heart Failure Questionnaire (for patients enrolled prior to protocol version 2, baseline MLHFQ will be administered at re-consent (+/-4 weeks).
 5. This will be a double blinded placebo control study design. All participants will be randomized 1:1 to sildenafil or placebo for a total of 12 months therapy.
 6. Sildenafil will be initiated at 5 mg 3 times per day for the first week, and titrated to 10 mg 3 times per day for the second week and 20 mg 3 times per day from the 3rd week to the end of the study period. The patients will be required to check their pulse rate and blood pressure daily during the first month of drug therapy. Patient who experience hypotension (blood pressure < 90/50 plus symptoms such as dizziness) during dose titration will be asked to remain on the previous tolerated dose. Patients who cannot tolerate 10 mg 3 times daily will be asked to withdraw from the study and will be asked to

- continue checking their blood pressure for three days after stopping the medication.
7. After 12 months (+/- 4 weeks) of therapy, all tests listed in #3 and #4 will be repeated.
 8. These same tests listed in #3 and #4 will be repeated for the patients who have follow-up up to 24 months (+/- 4 weeks).
 9. Adverse event and compliance monitoring: During the first month of enrollment (initiation and dose titration), adverse events will be collected by subject report and by weekly telephone or email interview (± 7 days) with dedicated research personnel. For the rest of the study period, adverse events will be collected by subject report and by monthly telephone or email interview (± 14 days) with dedicated research personnel. The research personnel will be responsible for sending out the monthly supply of medications and obtaining a count of the remaining number pills as a measure of compliance. All participants will be provided with a pamphlet containing all the side effects of sildenafil, and contact information of research team for reporting any adverse event or concerns about the study.
Up to three voicemail messages will be left for each follow-up.

H. Statistical analysis and power considerations:

Sample size and power

We have determined that a total of 40 patients who complete the study (20 patients in the treatment arm and 20 patients in the placebo) will adequately power the study accounting for approximately a 10% attrition rate. In a prior

study from the Mayo Clinic,¹³ the distribution of MRE stiffness score in the adult Fontan population was $4,900 \pm 1,100$ Pa. Assuming that the standard deviation of MRE is 1,000 both for before and after treatment measures, and that the within subject correlation between before and after measures is at least moderate in strength and positive (i.e. $\rho \geq 0.5$), then the variance in the difference between pre- and post-treatment MRE stiffness score is no more than 250 Pa. A sample of 40 patients in the treatment arm will provide 80% power for a two-sided two-sample t-test with a 0.05 Type I error rate to detect a mean difference of at least 500 Pa in treatment effect, as measured by the difference within patient MRE stiffness score.

Interim Analysis

An interim analysis of subjects who have completed 12 months of Sildenafil vs. Placebo therapy will be conducted at the end of the grant period (August 2019). Those still on Sildenafil vs. Placebo at that time will remain blinded until their completion of 12 months on Sildenafil vs. Placebo.

I. Human studies issues (consent or research authorization)

Consent

An informed consent will be obtained from the patients at the time of enrollment in the study. The consent will authorize a member of the research team to contact each patient by phone, email, or questionnaire. The study participants will be notified of the very limited evidence supporting the use of sildenafil in this population.

Data and Safety Monitoring

The Food and Drug Administration approved Sildenafil for the treatment of pulmonary hypertension. The patients will be notified that the use of sildenafil in this study is off-label. We will implement an internal safety monitoring system consisting of two members (not immediately affiliated with the study) to review reported side effects of sildenafil at the mid-point and completion of the study. Finally, and as always, extreme caution and monitoring of study participants will be undertaken throughout the study and in follow up to ensure no untoward events as a direct result of the study substance. Please see data safety monitoring plan.

M. Literature cited

1. Fontan F and Baudet E. Surgical repair of tricuspid atresia. *Thorax*. 1971;26:240-8.
2. Rychik J. Forty years of the Fontan operation: a failed strategy. *Seminars in thoracic and cardiovascular surgery Pediatric cardiac surgery annual*. 2010;13:96-100.
3. Gewillig M. The Fontan circulation. *Heart*. 2005;91:839-46.

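### The ±4-week window for routine baseline tests (G, item 3) has no reference date and no pre-dose requirement, so a compliant baseline exercise test could be taken on treatment

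*Combined protocol and SAP*

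**What the plan says.** Section G, item 3 lists the routine tests as "transthoracic echocardiogram, electrocardiogram, cardiopulmonary exercise test, complete blood count, chemistry panel, INR, alpha-fetoprotein" and describes them as "baseline tests (\pm 4 weeks) as part of standard clinical care". It names no date from which the four weeks are counted, and it does not say that the tests come before study drug. The same item extends the early side: "Baseline clinical tests performed within 6 months prior to enrollment will be accepted as part of the study". It also treats the tests as optional: "Any routine standard clinical tests or procedures that are not completed will not be considered a deviation".

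Other places bear on timing:

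- **G, item 9** sets weekly contact as follows: "During the first month of enrollment (initiation and dose titration". This ties enrollment to the start of dosing.
- **G, item 6** has two one-week lower steps and then "20 mg 3 times per day from the 3rd week to the end of the study period".
- **E(i)** requires a "baseline liver magnetic resonance elastography (MRE) prior to the initiation of phosphodiesterase-5 inhibitor (sildenafil". This ordering rule is written for the MRE only.
- **G, item 4** lists further baseline imaging, ultrasound, biomarkers and a questionnaire. It gives no window, except for the questionnaire in patients enrolled before protocol version 2.
- **G, item 7** repeats the item 3 and item 4 tests at 12 months.
- **F(i)** says that the use of pulmonary vasodilators in Fontan patients "results in increased cardiac output and exercise tolerance by promoting forward flow in the Fontan circuit".

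**The concern.** A baseline measured after the first dose is a post-randomization value. In the sildenafil arm it may already contain some drug effect; in the placebo arm it cannot. Subtracting it from the 12-month value removes that part of the effect from one arm only, so the difference between arms moves toward zero.

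The exercise test matters most here, because it is under the item 3 window and F(i) expects exercise tolerance to change. The echocardiogram may be exposed too, through the expected change in cardiac output. Nothing in the documents predicts an early effect on blood count, INR or alpha-fetoprotein.

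At stake is supporting evidence that sildenafil improves flow and function. With 20 completers planned per arm, there is little precision to spare on such measures.

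**Working it through.** The plan gives no figure for this point. Its only power statement (Section H) concerns MRE stiffness and is not an input here.

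**1. What the two-sided window adds.** If the reference date is enrollment, the early four weeks are already covered by the 6-month look-back. The only thing the ± window adds is permission to test up to four weeks late. Item 9 places initiation and titration in that same month.

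**2. Day count.** Suppose dosing starts on the reference date and the patient titrates on schedule (item 6). Days 1–7 and 8–14 are the two lower steps, and the top dose starts on day 15. A test on day 28 then follows 28 days of drug, of which 28 − 14 = 14 are at the top dose. If dosing starts d days after the reference date, the figures become 28 − d and 14 − d. With d of 14 or more there is no time at the top dose before the window closes; with d of 28 or more there is no exposure at all. The conclusion therefore depends on the date the protocol leaves out.

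**3. Effect on a comparison between arms.** Let Δ be the true 12-month effect, q the share of sildenafil patients whose baseline is on drug, and e the share of Δ present by then. The drug effect in the mean baseline of the sildenafil arm is q × e × Δ; in the placebo arm it is 0.

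- Change from baseline: Δ − q·e·Δ = Δ(1 − q·e).
- Adjustment for baseline with regression slope b: Δ(1 − b·q·e), a smaller loss when b is between 0 and 1.
- Unadjusted 12-month values: Δ, with no loss.

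**4. Size for change from baseline.** Both q and e are assumptions. The last column takes an endpoint that would have 80% power undiluted (two-sided 0.05, unchanged SD) and computes Φ[r(1.960 + 0.842) − 1.960] with r = 1 − q·e.

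| q | e | Loss q·e | Retained r | Power |
|---|---|---|---|---|
| 10% | 25% | 2.5% | 97.5% | 78% |
| 25% | 50% | 12.5% | 87.5% | 69% |
| 50% | 50% | 25% | 75% | 56% |
| 50% | 100% | 50% | 50% | 29% |

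The 80% starting point is for illustration only; the plan claims no power for these tests. If every baseline test precedes the first dose, q = 0 and nothing is lost.

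**The case against.** Much can be said in the plan's favor, and most of it limits the point rather than removing it.

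- **The reference date is assumed.** Only a parenthesis in the adverse-event item links enrollment to dosing. If the window is counted from consent or a screening visit, exposure may be short or nil. This stands, and it is why the conclusion is conditional. The missing date still needs to be supplied.
- **Eligibility probably forces some tests early.** Item 2 excludes severe ventricular dysfunction, severe valve regurgitation and severe renal dysfunction. Deciding these would normally need cardiac imaging and chemistry beforehand, and item 3 accepts such results as baseline. This largely stands for echocardiogram and chemistry, although item 2 names no test or date. It does not cover the exercise test.
- **No analysis of these tests is specified.** Section H describes only the MRE comparison, and item 3 tests are used if available. This stands. The bias arises only if change from, or adjustment for, baseline is used; the 12-month repeat invites that but does not prescribe it.
- **Speed of effect is undocumented.** F(i) gives no time to onset, and the titles of its cited studies name endothelin blockade and inhaled iloprost, not sildenafil. So e could be small.

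A reader might infer that all the mechanistic measures share the exposure. The documents do not support that. Item 4 has no such window apart from the re-consent questionnaire, which is a separate matter. Item 4a also brackets cardiac MRI and 4D flow with the MRE, so E(i) probably protects them if they are acquired together. Ultrasound and biomarkers simply have no stated timing.

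**Conclusion.** The point holds in a limited form and is minor. Item 3 does not require its baseline tests before the first dose, and its two-sided window has no reference date. On the reading that item 9 suggests, an on-treatment baseline exercise test, and possibly echocardiogram, complies with the protocol. A change-from-baseline contrast for that test would then be attenuated by q × e, from about 2.5% to 50% over the range shown. Both quantities are unknown, and nothing in the documents makes the upper end more likely than the lower.

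Two stronger inferences are not supported. One is that baselines have in fact been contaminated: the rule permits late tests, but the documents do not say that any occurred. The other is that the primary result is at risk: the MRE must precede sildenafil, so its comparison is unaffected. The mechanism described here also cannot create a false drug effect, since it can only hide part of a real one.

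**What to change.** **Text.** In item 3, replace the ±4-week window with: *before the first dose of study drug; tests up to 6 months before enrollment are accepted*. Add to item 4 that its baseline tests also precede the first dose. Handle the re-consent questionnaire separately.

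**Patients already enrolled.** Compare each baseline test date with the first-dose date in both arms. Do not use a test dated after the first dose as baseline; where an acceptable pre-enrollment result exists, use that. State how same-day tests are treated. Fix the rule before any unblinding, including for the interim analysis planned for August 2019. If no test proves late, the concern closes.

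**Cost.** A short amendment and a check of dates, with no new data collection. A few first doses may wait for a test, and some secondary baseline values will be lost. Patients who lose a baseline can still contribute to an unadjusted comparison of 12-month values.

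### The titration hold rule in item 6 requires symptoms, so a symptom-free reading below the 80/50 entry limit does not stop the next dose step, and item 9's ±7-day window guarantees no contact before the first step

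*Combined protocol and SAP*

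**What the plan says.** All places are in section G (Study design) of the combined protocol and SAP unless noted.

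- **Dose steps (item 6).** 5 mg three times daily in week 1, 10 mg in week 2, and 20 mg from week 3 to the end.
- **Hold rule (item 6).** The trigger is given as "Patient who experience hypotension (blood pressure < 90/50 plus symptoms such as dizziness) during dose titration". The action, once that trigger is met, is that the person "will be asked to remain on the previous tolerated dose". A patient who cannot tolerate 10 mg three times daily is withdrawn; no blood pressure level is attached to that rule.
- **Home readings (item 6).** "The patients will be required to check their pulse rate and blood pressure daily during the first month of drug therapy".
- **Entry limit (item 2).** "we also excluded patients with hypotension at baseline (BP $<$ 80/50 mmHg", with no symptom condition.
- **Contacts (item 9).** "During the first month of enrollment (initiation and dose titration" is the period covered, and in it "adverse events will be collected by subject report and by weekly telephone or email interview (± 7 days". No anchor day is given.
- **Other routes (item 9).** The patient pamphlet carries "contact information of research team for reporting any adverse event or concerns about the study". For patients who do not answer: "Up to three voicemail messages will be left for each follow-up".
- **Oversight (section I, Data and Safety Monitoring).** General caution and monitoring are promised, two people not immediately affiliated with the study review side effects at mid-point and completion, and the reader is referred to a separate data safety monitoring plan.

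**The concern.** Patients must measure blood pressure every day while the dose is doubled twice, but the supplied text attaches no consequence to a low reading unless the patient also feels unwell. A level low enough to bar someone from entry can be seen at home a week later, and the written rule still lets the next step go ahead. The supplied text does not say that readings are recorded, sent in or looked at before a step. The item 9 interviews collect adverse events and do not mention blood pressure.

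The weekly contacts might be expected to catch such a reading. Their window is as wide as a dose step, however, and the text does not say that the dose waits if the patient is not reached.

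What is at stake is participant safety: an off-label vasodilator is being titrated in patients whose circulation the Rationale describes as having low cardiac output. Home measurement is the only blood pressure monitoring that the text describes during titration. Acting on a symptom-free low reading before a step depends on the patient choosing to report it or staff choosing to ask. The gap does not bear on the sample size calculation or the type I error rate.

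**Working it through.** **1. The hold rule.** A reading below 80/50 is also below 90/50, provided both limits are read the same way. The blood pressure half of item 6's condition is then met, and symptoms are the only missing element. Without them the rule does not apply.

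**2. Dose calendar.** Inputs are the item 6 doses; the assumption is that day 1 is the first dose.

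- Days 1-7: 5 × 3 = 15 mg/day
- Days 8-14: 10 × 3 = 30 mg/day
- From day 15: 20 × 3 = 60 mg/day

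The steps therefore fall on days 8 and 15.

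**3. Contact windows.** Each window is the due day ± 7 (item 9). The due days are not stated, so two anchors are assumed. Both start the contact clock at first dose, and windows are cut at day 1.

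| Contact | Anchor A: due | Window | Anchor B: due | Window |
|---|---|---|---|---|
| 1 | 7 | 1-14 | 8 | 1-15 |
| 2 | 14 | 7-21 | 15 | 8-22 |
| 3 | 21 | 14-28 | 22 | 15-29 |
| 4 | 28 | 21-35 | 29 | 22-36 |

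**4. Day-8 step.** Contacts on days 14, 21, 28 and 35 (A) or 15, 22, 29 and 36 (B) all comply, and all fall after day 8. No contact is guaranteed before this step.

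**5. Day-15 step.** The latest first contact is day 14 (A) or day 15, the step day itself (B). So not every contact can fall strictly after this step. But contact 1 on any of days 1-7 with contact 2 on any of days 15-21 complies under both anchors and leaves days 8-14, the whole 10 mg week, without a contact.

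**6. Longest compliant stretch between contacts.** This is the latest day of one contact minus the earliest day of the one before it, minus 1.

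- A: contact 2 on day 7 and contact 3 on day 28 give 28 − 7 − 1 = 20 days (days 8-27). Contact 1 can be on day 6, so the order is kept.
- B: contact 1 on day 1 and contact 2 on day 22 give 22 − 1 − 1 = 20 days (days 2-21).

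**7. Would a narrower window be enough?** No. At ±3 days the first contact can be as late as day 10 (A) or 11 (B). At ±2 days it can be day 9 or 10. All of these follow the day-8 step. With contacts on exactly days 7 and 14, each step is preceded by one. Placing the contact before the step closes the gap; a tighter tolerance alone does not.

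**8. Cost of a delay.** Assuming a 365-day course, planned days at 60 mg/day are 365 − 15 + 1 = 351. One week of delay costs 7/351 = 2.0%.

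**The case against.** The strongest reply is that the rule is a clinical choice and that action limits may be written elsewhere.

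- **The symptom condition may be deliberate.** Item 2 admits a patient with systolic 80-89 and diastolic 50 or above, and requiring symptoms at that level is reasonable. This stands, and no change is proposed there. A reader might infer that items 2 and 6 contradict each other. They do not: one governs entry and the other titration.
- **Other documents may hold a rule.** The data safety monitoring plan is the natural place for one, and the pamphlet may tell patients which readings to report. Neither was supplied, so only the silence of the supplied text is established. A reader might infer that the trial has no such rule at all; that cannot be concluded.
- **Patients can call at any time.** True, and item 9 counts subject report as a source of adverse events. That is a route for reporting and does not hold the dose.
- **The timing is a worst case.** Also true. The anchors are assumed, and the 20 days need one contact at its earliest and the next at its latest. A reader might infer that all contacts can fall after both steps; step 5 of the working shows that this fails for the day-15 step.
- **A trigger on either value alone would go too far.** Systolic below 80 or diastolic below 50 would flag 110/48, and the documents do not say that item 2 is meant that way. The fix therefore follows item 2's own reading.
- **Few patients may benefit.** The document is dated July 31, 2019, and section H plans an August 2019 analysis of 12-month completers. Some patients are past titration, and how many remain is unknown.

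**Conclusion.** The concern holds for the supplied text. A symptom-free home reading below item 2's 80/50 limit does not hold the next dose step, and no scheduled contact is guaranteed before the day-8 doubling. Before the day-15 doubling, one contact falls by day 14 or by day 15 depending on the anchor, but none need fall in the 10 mg week. The compliant limit is 20 days without a scheduled contact under either anchor.

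This rests on day 1 being the first dose, on the contact clock starting with it, and on the two assumed anchors. The documents give no blood pressure distribution, so neither the number of patients affected nor any harm can be estimated. It is a safety improvement to consider, held with medium confidence, because an unseen document may already cover it.

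**What to change.** Apply to both arms.

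**Item 6, add:** A home reading below 80/50 mmHg, read the same way as in the item 2 exclusion and confirmed on one repeat after rest, is reported to the study team the same day, with or without symptoms. The dose is not increased until a study clinician blinded to arm has recorded proceed or hold. Such a hold alone does not count as failure to tolerate 10 mg three times daily.

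**Item 9, change:** Place the first two existing contacts in the 2 days before each planned step (days 6-7 and 13-14). Staff ask for and record the lowest home reading on the current dose. The step waits until the contact is made, with prompt repeat attempts and clinician review if the patient is not reached within 7 days. The 2-day and 7-day values are proposals for the team to set.

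**Cost:** A short amendment, one data field, and two contacts on a tighter window, plus a line in the pamphlet if it lacks one. No new dose level is needed, because item 6 already allows a patient to stay on a lower dose. The downside is slightly later titration in an unknown number of patients, at 2.0% of planned full-dose days per week of delay. Only patients still to be titrated benefit.

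If the data safety monitoring plan or the pamphlet already contains an equivalent rule, cite it in item 6 instead.

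### Patients who cannot tolerate 10 mg three times daily are asked to leave the study, not only the drug, so the visible plan has no month-12 MRE for them (probably few patients; cheap to improve)

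*Combined protocol and SAP*

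**What the plan says.** G.5 randomises patients 1:1, double blind, to 12 months of sildenafil or placebo. G.6 then titrates from 5 mg to 10 mg to 20 mg three times daily, starting weeks 1, 2 and 3. Two adjacent sentences of G.6 deal with poor tolerance:

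- The first covers symptomatic hypotension. Such a patient "during dose titration will be asked to remain on the previous tolerated dose", which is a rule about dose.
- The second is a rule about leaving: "Patients who cannot tolerate 10 mg 3 times daily will be asked to withdraw from the study". The one further step it gives this group is to "continue checking their blood pressure for three days after stopping the medication".

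The outcome scan is tied to treatment. Synopsis E(ii): "A second MRE will be performed after 12 months of therapy". G.7: "After 12 months (+/- 4 weeks) of therapy, all tests listed in #3 and #4 will be repeated".

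Section H counts patients in the same way. The sample size is "a total of 40 patients who complete the study (20 patients in the treatment arm and 20 patients in the placebo" arm), with about 10% attrition. The interim analysis uses "subjects who have completed 12 months of Sildenafil vs. Placebo therapy". Section H defines no final analysis set and no method for missing outcomes.

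**The concern.** The withdrawal rule acts after randomisation, and its trigger may depend on the assigned treatment. Blinding means the same rule applies in both arms, but it does not make the event equally frequent in both. If patients who cannot tolerate the drug would also have had a different stiffness course, losing more of them from one arm would bias the 12-month comparison. The attrition allowance replaces lost numbers; it does not address selective loss. A scan that is never done cannot be recovered at analysis. If it is done, an analysis of completers of therapy remains available as well.

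**Working it through.** **1. Is there a route to a month-12 MRE?** G.6 takes these patients out of the study at about the second week of titration. E(ii) and G.7 schedule the repeat scan after 12 months of therapy, which they do not reach. G.8 covers only patients who have follow-up to 24 months and does not bring withdrawn patients back. No other visible section does.

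**2. Inputs.** The plan has no figure of its own for this rule, so the size must be illustrated.

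- From section H: SD 1,000 Pa before and after, pre-post correlation 0.5, target 500 Pa, two-sided 0.05 two-sample t-test.
- SD of change = 1,000 × √(2 × (1 − 0.5)) = 1,000 Pa. With this SD the stated 80% power is not reproduced: the t-test gives 34% at 20 per arm and 60% at 40 per arm. That is a separate matter and does not bear on this point.
- Assumed, not in the documents: 40/0.9 = 44.4, taken as 22 randomised per arm; no true effect; k withdrawals; correlation r between intolerance and a worse stiffness change, from −0.5 to 0.5.

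**3. Shift in the between-arm difference.** Remove the k most intolerant of 22 sildenafil patients:

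shift = −r × SD × (sum of the top k expected normal order statistics) / (22 − k)

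- k = 1: 1.910/21 = 0.0909, so −91r Pa, or 45 Pa in size at |r| = 0.5.
- k = 2: (1.910 + 1.458)/20 = 0.168, so −168r Pa, or 84 Pa in size at |r| = 0.5.

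A negative shift favours sildenafil. A negative r reverses the sign.

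**4. Simulation with the pooled t-test.**

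| Withdrawn, sildenafil/placebo | Shift at r = 0.5 (Pa) | Rejection at r = 0.5 |
|---|---|---|
| 1/0 | −45 | 5.4% |
| 2/0 | −84 | 6.0% |
| 2/1 | −39 | 5.6% |
| 1/1 | 0 | 5.3% |
| 2/2 | 0 | 5.5% |

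At r = 0 the shift is about 0 and rejection is 5.0–5.1%. The mean standard error for 1/0 and 2/0 is 300–307 Pa. The balanced rows have no bias yet still reject 5.3–5.5%, so part of the excess comes from always removing exactly the most extreme patients.

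**5. Sensitivity to the SD.** The shift scales with the SD of change. At a pre-post correlation of 0.75 the SD is 1,000 × √(2 × 0.25) = 707 Pa, and two withdrawals give at most 84 × 0.707, about 60 Pa.

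**6. Cost of keeping these patients.** If off-drug patients get no benefit, a true 500 Pa effect becomes 500 × 21/22 = 477 Pa or 500 × 20/22 = 455 Pa. At SD 1,000 Pa and 22 per arm, power is then 34.0% or 31.3%. Analysing completers only (21 or 20 against 22), with losses unrelated to change, gives 36.0% or 35.2%. The loss is 2 or 4 percentage points.

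**The case against.** Several points on the other side stand.

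- **Few patients.** Those who fail 20 mg but tolerate 10 mg stay in, and under G.2 "we also excluded patients with hypotension at baseline". That exclusion is only partial: it uses 80/50 mmHg, while titration hypotension is below 90/50 with symptoms.
- **Undocumented inputs.** The documents give no intolerance rate, no imbalance between arms and no link between intolerance and stiffness. Every figure for the shift is an illustration.
- **The treatment question.** E(ii) and G.7 consistently ask about change after 12 months of therapy. Including patients who stopped early answers a somewhat different question, and the 23–45 Pa dilution is of the same order as the shift avoided. This bears on which analysis is primary. It is not a reason to skip the scan, because both analyses are possible only if the scan is done.
- **Unseen text.** Section I refers to a data safety monitoring plan that is not in the documents, and consent pages were removed from this copy. A follow-up rule could sit in either, so the point is limited to the visible plan.

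A reader might also infer that G.6 contradicts itself, since hypotension at 10 mg seems to mean both staying on 5 mg and withdrawing. The text does not support that reading. The two sentences read naturally as a general rule with a minimum dose: hypotension at 20 mg means staying on 10 mg, and failure at 10 mg means stopping. The wording is ambiguous at that one step and no more.

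**Conclusion.** The point holds as a gap in retention. Following the visible plan loses the month-12 MRE of randomised patients for a reason that may depend on treatment. Confidence is medium, because of the unseen text.

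The likely size is small. With one or two sildenafil-only withdrawals and the assumptions above, the shift is at most about 45 or 84 Pa in either direction. The larger figure is 17% of the 500 Pa target and well under one standard error. It is zero if these patients change as the others do, and about zero if losses are balanced.

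Two stronger conclusions are not supported. One is that the result will be biased towards sildenafil: the direction cannot be derived from the documents. The other is that type I error is materially inflated: the 5.4% for one withdrawal is almost matched by 5.3% in the unbiased 1/1 case. Placing the whole planned attrition of about four patients on sildenafil gives up to 154 Pa, but nothing in the documents points to that case.

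**What to change.** - **G.6:** ask patients who cannot tolerate 10 mg three times daily to stop study drug instead of leaving the study. Invite them, in both arms, to the month-12 MRE and tests; they may decline.
- **E(ii) and G.7:** time the repeat tests at 12 months (+/- 4 weeks) from the start of study drug.
- **Section H:** make the primary comparison all randomised patients with a month-12 MRE, in their assigned arm, with completers of therapy as a sensitivity analysis.
- **G.6, minor clarification:** state a single instruction for hypotension at the 10 mg step. The natural reading is to stop drug; the choice belongs to the clinical team.

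The cost is wording in four places, a month-12 visit for a few off-drug patients using tests already planned for the others, and the slight dilution shown in step 6. Nobody is asked to continue a drug they cannot tolerate.
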